### 2.2.2 Treatment Groups

For Final DBL analysis, the summaries will be performed by treatment sequence. For some safety summaries (e.g. exposure-adjusted) the 'switch' treatment may be summarized separately.

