#### 4.2.1.2 Mixed-effects repeated measures model

Endpoints with continuous data type expected to be normally distributed (e.g, [REDACTED]) will be analyzed using a mixed-effects repeated measures model (MMRM) with stratification factor and analysis visit as factors; and weight, baseline value, baseline by visit interaction as covariates. An unstructured correlation matrix will be used thus allowing adjustment for correlations between time points within subjects.

SAS code for mixed model:

```
proc mixed data=aaa;  
class USUBJID AVISITN STRATA;  
model CHG= STRATA AVISITN WEIGHT BASE BASE*AVISITN  
/ s ddfm=kr;  
lsmeans AVISITN / diff cl;
```

repeated AVISITN / type=un subject=USUBJID;

Run;

In case the MMRM model does not converge the following sequential steps will be used:

1. change ddfm=kr to ddfm=bw. If still no convergence, perform step 2.
2. change type=un to type=cs. If still no convergence, perform step 3.
3. remove covariates in the following order until convergence: WEIGHT, BASE\*AVISITN, STRATA.

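### If the unstructured MMRM fails to converge, the SAP's fallback first changes something that cannot help, then moves to compound symmetry with model-based standard errors, which can make intervals for visit differences wrong in both directions

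*SAP*

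**What the plan says.** SAP 4.2.1.2 states: "An unstructured correlation matrix will be used thus allowing adjustment for correlations between time points within subjects". The code agrees ("repeated AVISITN / type=un subject=USUBJID") and uses Kenward-Roger degrees of freedom. It asks for "lsmeans AVISITN / diff cl", that is, visit means and all pairwise visit differences with confidence limits.

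On non-convergence there are three sequential steps. The first swaps Kenward-Roger for between-within degrees of freedom ("change ddfm=kr to ddfm=bw. If still no convergence, perform step 2"). The second replaces the unstructured matrix by compound symmetry ("change type=un to type=cs. If still no convergence, perform step 3"). The third takes out weight, then baseline by visit, then stratum.

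The procedure call is "proc mixed data=aaa", with no EMPIRICAL option, and no step adds one. No structure between unstructured and compound symmetry is listed. Protocol 12.5.1 specifies unstructured covariance for the continuous secondary endpoints and gives no fallback.

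**The concern.** The REML likelihood depends on the mean model and the covariance parameters. The degrees-of-freedom method is not part of it, so step 1 reruns the same optimisation. Because the steps are sequential, the Kenward-Roger adjustment then stays off in steps 2 and 3.

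Step 2 assumes the same variance at every visit and the same correlation at 4 and 48 weeks apart. With model-based standard errors and complete data, every visit difference then gets essentially the same variance, whatever the gap. If correlation really decays with time, that common value is too large for neighbouring visits and too small for distant ones. At stake are the long-term change contrasts that the code prints, such as Week 16 to Week 52.

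**Working it through.** The documents state no figure on this point, so there is none to reproduce.

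**Inputs from the documents.** 190 patients per group (SAP 3); 10% dropout (Protocol 5); two-sided 5% (SAP 2.1). Post-baseline visits from SAP Table 4-1: seven for SF-36 and FACIT (Weeks 4, 8, 12, 16, 24, 28, 52), eight for mNAPSI, nine for LEI/LDI/PASI, and thirteen on the four-weekly grid.

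**Covariance parameters.** Unstructured needs J(J+1)/2: 28, 36, 45 and 91 for 7, 8, 9 and 13 visits. Compound symmetry needs 2.

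**Assumed.** The true within-patient covariance, which is varied below.

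**Large-sample check, complete data.** Let v be the mean variance and c the mean covariance over the visits.

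- Variance of a difference under compound symmetry: 2(v - c)
- True variance of visit j versus k: s_jj + s_kk - 2 s_jk
- SE ratio r = square root of (first / second)
- Coverage of the nominal 95% interval: 2Φ(1.96 r) - 1

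Worked case: seven visits, variance 1, correlation 0.9 per 4 weeks. The mean correlation is c = 0.647, so compound symmetry gives 2(1 - 0.647) = 0.706 for every difference.

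- Week 4 v 8: true 2(1 - 0.9) = 0.200; r = 1.88; coverage about 100%
- Week 16 v 52 (nine steps): true 2(1 - 0.387) = 1.225; r = 0.76; coverage 86.3%
- Week 4 v 52 (twelve steps): true 2(1 - 0.282) = 1.435; r = 0.70; coverage 83.1%

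SE ratio (coverage, %), constant variance, seven visits unless stated:

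| Assumed correlation (k = gap in weeks / 4) | Week 4 v 8 | Week 16 v 52 | Week 4 v 52 |
|---|---|---|---|
| Constant 0.6 | 1.00 (95.0) | 1.00 (95.0) | 1.00 (95.0) |
| 0.5 + 0.25 × 0.8^k, with 0.25 visit-level noise | 1.14 (97.5) | 0.91 (92.7) | 0.90 (92.2) |
| Same, mNAPSI grid (8 visits) | 1.15 (97.6) | 0.93 (93.0) | 0.91 (92.6) |
| 0.4 + 0.6 × 0.8^k | 1.67 (99.9) | 0.80 (88.5) | 0.77 (87.1) |
| 0.9^k | 1.88 (100) | 0.76 (86.3) | 0.70 (83.1) |
| 0.95^k | 2.01 (100) | 0.74 (85.2) | 0.66 (80.6) |

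On thirteen visits, with correlation 0.80-0.95 per visit and the SD constant or rising up to 1.5-fold, the ratios are 0.70-0.82 for Week 16 v 52 (83-89%) and 0.65-0.79 for Week 4 v 52 (80-88%).

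**Single-visit means.** With constant variance the Week 52 mean keeps 95%. If the SD rises linearly by 30% over the seven visits, r = √(1.3325/1.69) = 0.89 and coverage is 91.8%. If it rises by 50%, r = √(1.5903/2.25) = 0.84 and coverage is about 90%.

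**Simulation of the SAP's mean model under compound symmetry.** One arm of 190, seven visits, about 10% dropout depending on the last observed value, 1,000 runs (Monte Carlo error about 1 point). Coverage for Week 4 v 8 / 16 v 52 / 4 v 52:

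| True correlation | Model-based SE | Sandwich SE |
|---|---|---|
| Constant 0.6 | 96.2 / 95.1 / 95.3 | 95.2 / 94.5 / 95.1 |
| 0.4 + 0.6 × 0.8^k | 99.8 / 87.7 / 86.3 | 95.2 / 94.1 / 94.4 |
| 0.9^k | 100 / 82.9 / 80.0 | 95.1 / 93.2 / 93.1 |

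In the two decaying cases the two distant contrasts carried a bias of 0.016 to 0.030 SD in absolute size, which sandwich standard errors leave in place.

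**Do standard intermediate structures solve it?** TOEPH and ARH(1) count lag by visit order, so on the SF-36/FACIT grid Weeks 28 to 52 count as one lag, like Weeks 4 to 8. Fitting them to a true correlation of 0.8^k or 0.9^k (large sample) gives a Week 28 v 52 SE ratio of 0.74-0.77 and coverage of 86-87%. Compound symmetry gives 0.87 and 91%. They do well on Week 16 v 52 (about 94-95%), so they move the error to another contrast.

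**The case against.** The strongest reply is that the harm needs two things at once: the unstructured fit must fail, and the true covariance must differ from compound symmetry. That stands. Nothing in the documents shows that failure is likely. The count of 91 parameters applies only to a thirteen-visit endpoint. Of the named continuous secondary endpoints, only HAQ-DI could be on that grid; PASDAS needs SF-36 and so has at most seven visits.

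It also stands that purely autoregressive decay is an adverse assumption. A stable patient component plus measurement noise brings distant-visit coverage to about 92-93%. Nor is any numerical consequence of step 1 shown at about 190 patients per arm. It is an ineffective step rather than a harmful one.

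Two stronger readings are tempting but unsupported:

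- A reader might infer that the Week 16 tests are affected. SAP 1 limits this document to the final lock and says the Week 16 and testing-hierarchy analyses are not repeated. No listed objective tests Week 16 or Week 4 against Week 52.
- A reader might infer that the arms are pooled, because "model CHG= STRATA AVISITN WEIGHT BASE BASE*AVISITN" has no treatment term and the code no BY statement. SAP 2.2.2 says "For Final DBL analysis, the summaries will be performed by treatment sequence", and the code is a template that fits a within-sequence analysis.

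What the reply does not remove is that a prespecified fallback exists for the case in which it is triggered, and this one keeps standard errors that rely on an implausible pattern over 52 weeks.

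**Conclusion.** The point holds conditionally. Step 1 cannot cure non-convergence. If step 2 is reached and correlation decays with time, intervals for adjacent-visit differences are too wide (about 97-100% coverage). Those for distant differences are too narrow: about 83-93% for Week 16 v 52 and about 80-93% for Week 4 v 52. These ranges rest on assumed covariances. There is no loss if compound symmetry is true, and single-visit means are affected only if the variance changes. It would be wrong to say that all intervals are too narrow, or that the plan as written gives wrong intervals without the trigger. Only long-term, non-confirmatory estimates are touched, so this is a modest but worthwhile correction.

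**What to change.** - Delete step 1 and keep Kenward-Roger with the unstructured fit.
- Whenever a structure simpler than unstructured is used, including compound symmetry, add EMPIRICAL to the PROC MIXED statement (sandwich standard errors) with ddfm=bw.
- If an intermediate structure is tried before compound symmetry, prefer one defined on actual weeks. TOEPH or ARH(1) should not be used on an unequally spaced grid without EMPIRICAL.
- Report which structure was used for each endpoint.

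The cost is a few lines of SAP text and code. Where the fallback applies, the Week 16 v 52 interval widens by about 9% in the mildest seven-visit decay case above (1/0.914 = 1.09) and about 32% at 0.9 per 4 weeks (1/0.759 = 1.32), while adjacent-visit intervals narrow. Sandwich standard errors ran slightly under nominal for distant contrasts in the decaying cases (93-94%), and they do not remove the small bias that a misspecified covariance brings when data are missing at random.

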## 4.2.2 Analysis of binary (and categorical) data

### 4.2.2.1 Analyses of Frequencies

Summary statistics for discrete variables will be presented in contingency tables and will include count and frequency in each category. For  $n$  subjects, each at risk to experience a certain event with probability  $\pi$ , the crude incidence is estimated as  $p=x/n$ , where  $x$  is the number of subjects with the event.

If applicable, 95% confidence intervals for the relative frequencies will be derived as well based on the score method including continuity correction [Newcombe 1998](#):

With  $z$  as  $(1-\alpha/2)$ -quantile of the standard normal distribution (SAS:  $z=PROBIT(1-\alpha/2)$ ),  $n$  as total number of subjects (i.e. number of subjects in the denominator), and  $p$  as estimated crude incidence (number of subjects with event /  $n$ ) it is  $q=1-p$

Then the lower limit is

$$L = \max \left( 0, \frac{2np + z^2 - 1 - z\sqrt{z^2 - 2 - \frac{1}{n} + 4p(nq+1)}}{2(n+z^2)} \right)$$

and the upper limit is

$$U = \min \left( 1, \frac{2np + z^2 + 1 + z\sqrt{z^2 + 2 - \frac{1}{n} + 4p(nq-1)}}{2(n+z^2)} \right).$$

In addition, if  $L > p$  then  $L = p$  and if  $U < p$  then  $U = p$ .

For binary response variables (e.g. for ACR20/50/70, HAQ-DI responder, PASI 75, IGA response) the placebo-adjusted response rates including 95% confidence interval will be derived.

SAS code for risk difference:

Proc freq data=acr order=formatted;

Tables response\*trt/ riskdiff;

Run;

(Note the response value should be sorted with '1' ahead of '0'.)

Fisher's exact test will be applied to rare events (e.g., MCR), pairwise treatment group comparisons to placebo or active controls.

SAS code for Fisher's exact test:

```
Proc freq data=mcr order=formmatted;
```

```
Tables response*trt/Fisher;
```

```
Run;
```

If appropriate, an exact  $100*(1-\alpha)\%$  confidence interval ([Clopper-Pearson 1934](#)) will be obtained by using the SAS procedure PROC FREQ with the EXACT BINOMIAL statement. However, the confidence interval derived via the score method including continuity correction will be the default in safety analyses.

Figures will be provided for primary and secondary variables, with means displayed across time for all the treatment groups.

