12.4.2 Statistical model, hypothesis, and method of analysis

The statistical hypothesis for ACR50 being tested is that there is no difference in the proportion of subjects fulfilling the ACR50 criteria at Week 16 in i.v. secukinumab vs. placebo regimen.

Let p_j denote the proportion of ACR50 responders at Week 16 for treatment regimens j , $j=0, 1$ where

- 0 corresponds to placebo regimen,
- 1 corresponds to i.v. regimen,

In statistical terms, $H_0: p_1 = p_0$, $H_{A1}: p_1 \neq p_0$, for the i.v. secukinumab regimen, i.e.

H_1 : The i.v. secukinumab. regimen is not different to placebo regimen with respect to signs and symptoms (ACR50 response) at Week 16

The primary endpoint of ACR50 at Week 16 in the FAS will be evaluated using a logistic regression with treatment and randomization stratum (TNF α status –naïve or IR) as factors and weight as a covariate. Difference in marginal response proportions will be computed for comparisons of i.v. secukinumab vs. placebo regimen utilizing the logistic regression model fitted.

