## 1 Introduction

Data will be analyzed by Novartis according to the data analysis section 12 of the clinical study protocol. The statistical methodology is described below and any deviations from the protocol are documented. Additional detailed information regarding the analysis methodology is contained in the Appendix section.

This version of SAP covers the statistical and analytical plans of the CAIN457P12302 trial regarding the final DBL. As this is the Final DBL, analysis will only be done for long-term efficacy and safety. Analyses pertaining to Week 16 will not be repeated. Tables and listing for demographics, baseline disease characteristic, prior medication and medical history will not be reproduced. Any analyses related to the testing hierarchy will not be reproduced.

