### 1.1 Study Design

This multicenter study uses a randomized, double-blind, placebo-controlled, parallel-group design to study the efficacy, safety and tolerability of treatment with intravenous secukinumab in patients with active PsA.

The study population comprises approximately 380 patients with active PsA, despite current or previous NSAID, DMARD and / or TNF inhibitor therapy or intolerance to these therapies.

At baseline, patients will be randomized to one of the two treatment groups in a 1:1 randomization:

- **Group 1:** approximately 190 patients; These patients will receive secukinumab 6 mg/kg i.v. at Baseline (BSL), followed by the administration of secukinumab 3 mg/kg i.v. every four weeks starting at Week 4.
- **Group 2:** approximately 190 patients; These patients will receive i.v. placebo at BSL, Weeks 4, 8, and 12, followed by the administration of secukinumab 3 mg/kg i.v. every four weeks starting at Week 16.

This study will consist of 4 periods: a screening period (up to 10 weeks), treatment period 1 (total duration of 16 weeks) and treatment period 2 (total duration of 36 weeks) followed by a safety follow up period of 8 weeks after the end of treatment visit (i.e., Week 52).

To ensure a balance across both arms, patients previously treated with TNF-inhibitors will be stratified at randomization. No more than 25% of previously treated TNF-inhibitor patients will be enrolled in the study, with this cutoff applied to each group at randomization (no more than 48 patients per group).

Because PsA is considered a chronic disease with no ‘true’ and lasting placebo response, all patients, including those on placebo, will switch to open-label i.v. secukinumab at Week 16. However, all patients and investigators/ site staff will remain blinded to the original randomized treatment group assignment (i.v. secukinumab treatment or placebo).

[figure not shown]
An end of treatment visit (Week 52) will be done 4 weeks after last study treatment administration, and a post treatment follow-up visit (Week 60) is to be done 8 weeks after end of the treatment visit for all subjects (regardless of whether they complete the entire study as planned or discontinue prematurely).

All intravenous infusions will be performed at the study site and site personnel will administer the infusions to subjects.

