**Randomized treatment:**

- AIN457 6mg/kg - 3mg/kg
- Placebo

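### The SAP's risk-difference code has response in the rows, so it does not return the placebo-adjusted response rate that SAP 4.2.2.1 says it will derive

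*SAP*

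**What the plan says.** SAP section 4.2.2.1 (Analyses of Frequencies) states that for binary response variables, with ACR, HAQ-DI, PASI and IGA responses as examples, "the placebo-adjusted response rates including 95% confidence interval will be derived". The code offered for the risk difference opens with "Proc freq data=acr order=formatted" and requests "Tables response\*trt/ riskdiff". A note after it asks that response value 1 sort ahead of 0.

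Three other places in the SAP bear on whether this sentence belongs in this version:

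- Section 1 (Introduction), which limits this version to the final database lock: "Analyses pertaining to Week 16 will not be repeated".
- Section 1.1 (Study Design): "all patients, including those on placebo, will switch to open-label i.v. secukinumab at Week 16".
- Section 2.2.2 (Treatment Groups): "For Final DBL analysis, the summaries will be performed by treatment sequence".

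For the Week 16 primary endpoint, protocol section 12.4.2 uses a different method: "Difference in marginal response proportions will be computed for comparisons of i.v. secukinumab vs. placebo regimen utilizing the logistic regression model fitted". Protocol section 12.5.1 defines the estimand for the secondary binary endpoints in the same way.

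**The concern.** The prose and the code describe two different quantities. A placebo-adjusted response rate conditions on treatment: the probability of response on secukinumab minus the probability of response on placebo. With response as the row variable, the code conditions on response: the probability of being in a given arm among responders minus that among non-responders.

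The sorting note does not repair this. With response in the rows, it only makes responders the first row. It would select the response column only if response were the column variable, which suggests that `trt*response` was intended. No other SAP text overrides the layout.

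If the line is run as printed, a table labelled as a placebo-adjusted rate would carry both the wrong estimate and the wrong interval. The result would still look like a plausible treatment difference, so it could pass unnoticed.

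**Working it through.** **Inputs.** Planning rates at Week 16 come from SAP section 3.1.1 and Table 3-2:

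- ACR50: placebo 8.1%; secukinumab 35.9% or 39.6%.
- MDA: placebo 7.8%; secukinumab 27.7% or 32.4%.
- ACR20: placebo 27.4%; secukinumab 55.5% or 62.6%.
- 190 patients per arm, 1:1 allocation (SAP sections 1.1 and 3).

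Two things do not come from the documents. The first is standard SAS behaviour: the first variable in a TABLES request forms the rows, and RISKDIFF compares row proportions. The second is an assumption that the treatment labels in SAP section 2.2.2 are the formatted values. Then "AIN457 6mg/kg - 3mg/kg" sorts ahead of Placebo and is column 1. If placebo were column 1, only the sign would change.

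**The plan's own figure.** 35.9 − 8.1 = 27.8 points and 39.6 − 8.1 = 31.5 points, as in SAP section 3.1.1. Power at 190 per arm (two-sided 5%, two proportions) is above 0.9999 for both, consistent with the stated figure of about 99%. The treatment-by-response layout returns the same 27.8 and 31.5.

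**What the printed code returns.** Let p1 and p0 be the active and placebo rates, s = p1 + p0 and m = s/2. With equal arms:

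- P(active | responder) = p1/s
- P(active | non-responder) = (1 − p1)/(2 − s)
- Difference = (p1 − p0)/[s(2 − s)] = (p1 − p0)/[4m(1 − m)]

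**ACR50 at 35.9% vs 8.1%.** m = 0.220 and 4m(1 − m) = 0.6864, so the result is 0.278/0.6864 = 0.405. By expected counts, responders are 68.2 active and 15.4 placebo; non-responders are 121.8 and 174.6. Then 68.2/83.6 − 121.8/296.4 = 0.816 − 0.411 = 0.405, against 0.359 − 0.081 = 0.278.

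**All planning rates** (percentage points, Wald 95% CI on each 2×2 layout):

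| Endpoint and rates | Intended difference | Code as printed | Ratio |
|---|---|---|---|
| ACR50, 35.9% vs 8.1% | 27.8 (20.0 to 35.6) | 40.5 (30.5 to 50.5) | 1.46 |
| ACR50, 39.6% vs 8.1% | 31.5 (23.5 to 39.5) | 43.4 (33.8 to 52.9) | 1.38 |
| MDA, 27.7% vs 7.8% | 19.9 (12.5 to 27.3) | 34.1 (22.8 to 45.4) | 1.71 |
| MDA, 32.4% vs 7.8% | 24.6 (16.9 to 32.3) | 38.3 (27.8 to 48.8) | 1.56 |
| ACR20, 55.5% vs 27.4% | 28.1 (18.6 to 37.6) | 28.9 (19.2 to 38.7) | 1.03 |
| ACR20, 62.6% vs 27.4% | 35.2 (25.8 to 44.6) | 35.6 (26.1 to 45.0) | 1.01 |

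The ratio 1/[4m(1 − m)] depends only on the pooled rate: 2.78 at 10%, 1.96 at 15%, 1.56 at 20%, 1.19 at 30%, 1.04 at 40% and 1.00 at 50%.

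**Fisher's exact test.** The code in the same section has the same variable order, but its p-value does not change on transposing: 2.9 × 10⁻¹¹ either way for 68/190 vs 15/190.

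**The case against.** The syntax is hard to defend; the case on the other side is about consequence.

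- **No planned output at this lock.** SAP section 2.1 directs inferential placebo comparisons mainly to the first 16 weeks, section 1 says those analyses are not rerun, and section 2.5.3 presents later data as observed cases, with multiple imputation of ACR50 for the secukinumab arm only. Read together, these call for no placebo-adjusted efficacy table.
- **Carried-over text.** The same section mentions active controls, which this trial lacks. Table 4-2 gives baseline rules for X-ray and MRI, and Table 4-3 uses a 150 mg arm that does not exist here. The snippet may be an unused template remnant.
- **Illustrative size.** The figures above use Week 16 rates with a concurrent placebo arm. After Week 16 both sequences are on active drug, the documents give no Week 52 rates, and the distortion fades as the pooled rate nears 50%.
- **Direction is kept.** The printed code gives zero exactly when the true difference is zero, and otherwise has the same sign.
- **Nothing confirmatory is touched.** The primary test, testing hierarchy and power do not use this line.

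All of this stands as a limit on impact. It does not make the instruction correct: the sentence is worded as a commitment, the code beneath it yields something else, and the scope argument is itself a reason to remove the text.

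**Conclusion.** The concern holds. Followed as written, SAP section 4.2.2.1 produces an estimate and interval for a quantity other than the one it names. At the planning rates with equal arms, the overstatement is a factor of 1.38 to 1.46 for ACR50, 1.56 to 1.71 for MDA and 1.01 to 1.03 for ACR20. These are illustrations, not predictions of any final-lock output. They rest on 190 per arm, Week 16 rates and the secukinumab label sorting first.

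The sentence also does not fit a SAP version that leaves Week 16 alone and has no placebo group afterwards. The primary analysis, hierarchy, power and Fisher test are unaffected. The documents do not show that the line has been or will be run. It should be corrected, but it does not threaten the trial's main conclusions.

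**What to change.** Preferred: delete the placebo-adjusted sentence and its code from SAP section 4.2.2.1, since this version covers only the final lock.

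If the sentence is kept, replace the request with `tables trt*response / riskdiff(column=1);`. Order the levels so that secukinumab is the first row and response = 1 the first column, and state which period and treatment groups the comparison covers.

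In either case, check as a precaution that no existing output program, including those for the completed Week 16 analysis, used the transposed layout.

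The cost is one deleted sentence with its code, or one changed line, plus a program check. Design, sample size, testing hierarchy and primary analysis do not change.
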